3.14.1.6. Treatment of Overdose

A listing of patients reporting AEs related to overdosing of tirzepatide will be provided. Per protocol, any dose of study drug greater than the highest possible dose (15 mg) and estimated from where the patient is in the dose-escalation regimen or treatment-maintenance regimen within a 2-day time period will be considered an overdose and should be reported as an AE.

3.14.2. Patient Narratives

Patient narratives will be provided for all participants who experience any of the following “notable” events:

- death
- SAE
- pregnancy
- permanent discontinuation of study treatment due to AEs, or
- severe adverse events of special interest.

Patient narratives (patient-level data and summary paragraph) will be provided for participants in the randomized population with at least 1 notable event.

3.14.3. Special Safety Topics

3.14.3.1. Hypoglycemia

Clinically significant hypoglycemia (Level 2 or 3 hypoglycemia) will be summarized as the number of patients with at least one hypoglycemia, incidence, the number of total episodes, and the rate per 100 patient years during the study by treatment group if deemed necessary. Based on ADA (2022), Level 2 hypoglycemia is defined as a glucose less than 54 mg/dL (3.0 mmol/L), and Level 3 hypoglycemia is defined as a severe event characterized by altered mental and/or physical status requiring assistance for treatment of hypoglycemia; it is also referred to as severe hypoglycemia. Glucose measurements may not be available during such an event, but neurological recovery attributable to the restoration of glucose concentration to normal is considered sufficient evidence that the event was induced by a low glucose concentration.

Hypoglycemic episodes will be recorded on a specific eCRF. Information regarding severity, time of day, and investigator's opinion of relatedness to study drug and procedure will be listed. Hypoglycemic episodes will be recorded as an AE only if it meets serious criteria.

To avoid duplicate reporting, all consecutive hypoglycemic events occurring within a 1-hour period will be a single hypoglycemic event.

Hypoglycemia will be considered as an AESI. A listing of all events of serious or severe hypoglycemia may be provided, if deemed necessary. This listing will provide treatment allocation, clinical characteristics of the hypoglycemic event, and concomitant antihyperglycemic medications.

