# 1.3. Schedule of Activities (SoA)

1.5. Schedule of Acti		cs (	JUAJ													
Visit	1 a	2 a,b	3 a	4	5	6	7	8	9	10	11	12	13	14	801	ET
Week of Treatment	-6	-4	0	1	4	8	12	16	20	26	32	40	48	52	56	
Study Day/(Dose number)			0/(1)	7/(2)	28/(5)	56/(9)	84/(13)	112/(17)	140/(21)	182/(27)	224/(33)	280/(41)	336/(49)	364/ND	392/ND	
Visit Window (days)				±3	±3	±7	±7	±7	±7	±7	±10	±14	±7	±7	±7	
Fasting Visit	X		X	X	X	X	X	X	X	X	X	X	X	X	X	X
Administrative																
Informed consent	X															
Diabetes/therapy	X		X		X	X	X	X	X	X	X	X	X	X	X	X
Medical history	X															
Health habits (alcohol use, tobacco use)	X															
Cardiovascular risk factors history			X													
Alcohol use questionnaire (AUDIT)	X													X		X
Concomitant medications	X		X	X	X	X	X	X	X	X	X	X	X	X	X	X
Inclusion/Exclusion	X		X													
Randomization			X													
IWRS	X	X	X	X	X	X	X	X	X	X	X	X	X	X	X	X
BG meter/supplies, counseling (T2DM patients only) (resupply as needed)			X													
Diet, physical activity coaching			X		X	X	X			X		X				
Study diary, dispense			X		X	X	X	X	X	X	X	X	X	X		
Review diaries for BG values (T2DM patients only)			X	X	X	X	X	X	X	X	X	X	X	X	X	X
Subcutaneous injection training c			X	X												
Study drug and injection supplies, dispense d			X	X	X	X	X	X	X	X	X	X	X			
Participant returns study drug supplies					X	X	X	X	X	X	X	X	X	X		X
Drug accountability and compliance			X	X	X	X	X	X	X	X	X	X	X	X		X

Visit	1 a	2 a,b	3 a	4	5	6	7	8	9	10	11	12	13	14	801	ET
Week of Treatment	-6	-4	0	1	4	8	12	16	20	26	32	40	48	52	56	
Study Day/(Dose number)			0/(1)	7/(2)	28/(5)	56/(9)	84/(13)	112/(17)	140/(21)	182/(27)	224/(33)	280/(41)	336/(49)	364/ND	392/ND	
Visit Window (days)				±3	±3	±7	±7	±7	±7	±7	±10	±14	±7	±7	±7	
Fasting Visit	X		X	X	X	X	X	X	X	X	X	X	X	X	X	X
	Participant Demographics															
Age/Gender	X															
Race/Ethnicity	X															
						Cli	nical Var	iables								
Adverse events			X	X	X	X	X	X	X	X	X	X	X	X	X	X
Physical examination e	X															
Height	X													X		X
Weight	X		X		X	X	X	X	X	X	X	X	X	X	X	X
Waist circumference	X		X		X	X	X	X	X	X	X	X	X	X	X	X
Vital signs (BP, pulse rate, and body	X		X		X	X	X	X	X	X	X	X	X	X	X	X
temperature)			Λ		Λ	Λ	Λ	Λ	Λ	Λ	Λ	Λ	Λ	Λ	Λ	Λ
Dilated fundoscopic examination f	X															
						Diag	nostics (	Safety)								
Screening laboratory tests g	X															

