# 8.3.7.6. Hypoglycemia

Upon ICF signing, all participants will be educated about signs and symptoms of hypoglycemia and how to treat it. Additionally, at Visit 3 participants with T2DM will receive glucometers to monitor glycemia and will be trained on how to collect appropriate information for each episode of hypoglycemia in the study.

When diagnosing and categorizing an episode considered to be related to hypoglycemia, investigators should use definitions and criteria in accordance with the 2017 American Diabetes Association position statement on glycemic targets (ADA 2017), as described in Appendix 4 (Section 10.4).

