2.1. Summary of Study Design

Study I8F-MC-GPHR (GPHR) is a Phase 2, multicenter, randomized, double-blinded, placebo-controlled study that will investigate the effects of treatment with tirzepatide 5 mg, 10 mg, and 15 mg SC QW compared with placebo on NASH resolution with no worsening of fibrosis in patients with biopsy-proven NASH and fibrosis, with or without T2DM.

Figure GPHR.2.1 illustrates the study design.

[figure not shown]

Figure GPHR.2.1. Illustration of study design for Clinical Protocol I8F-MC-GPHR.

Study GPHR will consist of 3 periods:

- Screening (Visits 1 and 2)
- Treatment (Visits 3 to 14)
 - 4- to 20-week dose escalation (4-week for 5-mg group, 12-week for 10-mg group, 20-week for 15-mg group)
 - 32- to 48-week maintenance (48-week for 5-mg group, 40-week for 10-mg group, 32-week for 15-mg group)
- Safety follow-up (4 weeks post-treatment, through Visit 801)

The maximum total duration of the combined treatment periods is 52 weeks.

Enrichment Strategy

Participants with biopsy-proven NASH will be enrolled into this study. The study population will be enriched for participants who have T2DM, such that 40% to 65% of the total study population will consist of participants with NASH who have also been diagnosed with T2DM. The other 35% to 60% of the study population will consist of participants with NASH who do not have T2DM.

Participant Visit Scheme

Participants with a qualifying liver biopsy performed within 6 months of screening who meet the other required inclusion and exclusion criteria can participate in the study after evaluation of the histology by 2 central pathologists with experience in NASH to confirm presence of NASH and the study-specific histological inclusion criteria. Visit 2 will be omitted for these participants.

Participants without a qualifying liver biopsy will undergo assessments of their CAP and LSM at Visit 1 using TE to determine if they have a high probability of fatty liver disease with fibrosis. Participants meeting prespecified criteria for a high probability of fatty liver disease with fibrosis by TE will undergo a liver biopsy at Visit 2 to assess study eligibility, provided they meet all other required inclusion and exclusion criteria. Liver biopsies will be evaluated by 2 central pathologists with experience in NASH prior to Visit 3 to confirm presence of NASH and study-specific histological inclusion criteria.

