3.1. Population for Analyses

For purposes of analysis, [Table GPHR.3.1](#) defines the following analysis populations/data sets:

Table GPHR.3.1. Analyses Populations/Data Sets

Population/Data Set	Description
Entered population	All participants who sign informed consent
Randomized population	All participants who are randomly assigned to a treatment arm
Modified intent-to-treat (mITT) population	All randomly assigned participants who are exposed to at least 1 dose of study drug. In the event of a treatment error, participants will be analyzed according to the treatment they were randomized.
Efficacy analysis set (EAS)	Data obtained during treatment period from all randomized participants, excluding data after permanent study drug discontinuation. Participants will be analyzed according to the treatment they were randomized.
Exploratory analysis set (EXAS)	Data obtained during treatment period from mITT population participants who stay on study treatment for at least 36 weeks, excluding data after permanent study drug discontinuation.
Full analysis set (FAS)	Data obtained during treatment period from the mITT population, regardless of adherence to study drug.
Safety analysis set (SS)	Data obtained during treatment period plus the safety follow-up period from the mITT population, regardless of adherence to study drug.

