3.14. Safety Analyses

Unless specified otherwise, safety assessments will be based on the SS ([Table GPHR.3.1](#)). All events that occur between the date of first dose of study drug to the date of patient's safety follow-up visit or patient's end of study participation will be included, regardless of the adherence to study drug or availability of the end of treatment liver biopsy. For assessing the benefit and risk profile through 52 weeks, selected safety analyses will be conducted by utilizing safety data from first dose through the date of the 52-week visit.

The statistical assessment of homogeneity of the distribution of categorical safety responses among treatment arms will be conducted using Fisher's exact test, unless specified otherwise.

The mean change from baseline differences among treatments at all scheduled visits will be assessed via an MMRM using REML, unless specified otherwise. The model will include baseline T2DM status (Yes/No), the region (Japan, US including Mexico, and Europe including Israel), treatment group, visit and treatment-by-visit interaction as fixed effects, and baseline value of the safety parameter as a covariate. To model the covariance structure within patients, the unstructured covariance matrix will be used. If this model fails to converge, the covariance structures specified in Section [3.11.2.1](#) will be tested in order.

For selected safety parameters, time-to-first-event analysis via the Cox Proportional-Hazards model may be conducted. Patients without the event will be censored at the end of study participation. For patients experiencing the event, the "time-to-first-event" will be the time (in days) from first dose to first occurrence of the event.

Where necessary, the rate of events will be analyzed using a generalized linear mixed-effects model assuming the number of events follow a negative binomial distribution and with treatment as a fixed effect. The logarithm of days during the active treatment period will be adjusted as an offset to account for possible unequal treatment duration of follow-up between patients.

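### Hypoglycaemia is to be summarised over all participants, but only those with T2DM have home glucose meters, so pooled absolute rates understate those in T2DM

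*SAP*

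**What the plan says.** SAP 3.14.3.1 takes Level 2 and Level 3 hypoglycaemia together and plans the number of participants affected, incidence, total episodes and "the rate per 100 patient years during the study by treatment group if deemed necessary". Level 2 is defined by a glucose below 54 mg/dL (3.0 mmol/L). Level 3 is defined by the need for assistance, and a glucose reading may be absent.

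The section names no analysis set, so the general rule in SAP 3.14 governs: "Unless specified otherwise, safety assessments will be based on the SS". SAP 3.1 defines that set as "Data obtained during treatment period plus the safety follow-up period from the mITT population, regardless of adherence to study drug". It therefore holds everyone randomised and dosed, whatever their diabetes status.

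Monitoring is not the same for everyone. Protocol 8.3.7.6 states that "at Visit 3 participants with T2DM will receive glucometers to monitor glycemia" and adds training in recording episodes. The Schedule of Activities limits both the meter supplies and the review of diary glucose values to T2DM patients. Symptom education is universal: "Upon ICF signing, all participants will be educated about signs and symptoms of hypoglycemia and how to treat it".

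On the population mix, SAP 2.1 says that "40% to 65% of the total study population will consist of participants with NASH who have also been diagnosed with T2DM". The remaining 35% to 60% do not have T2DM.

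**The concern.** Level 2 exists only where a glucose value exists. Participants with T2DM have a meter at hand and record weekly fasting readings (Protocol 6.5.1.1). Those without T2DM contribute full patient-years to the denominator, but a non-severe episode at home will usually leave no glucose value behind. A pooled rate mixes a monitored group with a largely unmonitored one and describes neither.

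The absolute risk in the group that the protocol itself treats as exposed is at stake. Protocol 8.3.7.6 notes more hypoglycaemia with concomitant sulfonylurea, and Protocol 6.5.1.2 allows sulfonylurea and basal insulin as rescue. A pooled figure would understate that risk and could make the unmetered group look reassuring.

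No other planned output clearly fills the gap:

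- Under Protocol 8.3.7.6 and SAP 3.14.3.1, episodes go on a dedicated form and become adverse events only if serious. Non-serious Level 2 events will therefore not appear in the adverse event tables.
- The listing that shows concomitant antihyperglycaemic drugs is optional and covers serious or severe events.
- The T2DM subgroup in SAP 3.15 is for primary and secondary efficacy endpoints.

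**Working it through.** The documents state no expected hypoglycaemia rate, so there is no figure of the plan's own to reproduce.

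**Inputs**
- T2DM share of participants, s: 0.40 to 0.65 (SAP 2.1).
- Arm size: 196 randomised 1:1:1:1 (SAP 2.3), so 196 / 4 = 49.
- f, the recorded rate without T2DM divided by the recorded rate with T2DM. The documents do not give it; assumed 0, 0.10 and 0.25.
- Similar follow-up with and without T2DM, so that the share of patient-years equals s (assumption).

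**Dilution**

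Pooled rate / T2DM rate = s + (1 − s) × f. The inverse shows how many times larger the T2DM rate is.

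| f | s = 0.40 | s = 0.65 |
|---|---|---|
| 0 | 0.40, so 1/0.40 = 2.5 | 0.65, so 1/0.65 = 1.54 |
| 0.10 | 0.40 + 0.60 × 0.10 = 0.46, so 2.17 | 0.65 + 0.35 × 0.10 = 0.685, so 1.46 |
| 0.25 | 0.40 + 0.60 × 0.25 = 0.55, so 1.82 | 0.65 + 0.35 × 0.25 = 0.7375, so 1.36 |

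**Effect on the comparison between arms**

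Take assumed T2DM rates of 10 and 5 per 100 patient-years in two arms, with f = 0.
- s = 0.40: pooled 4.0 and 2.0. The ratio stays 2.0; the difference falls from 5 to 2.0.
- s = 0.65: pooled 6.5 and 3.25. The ratio stays 2.0; the difference falls from 5 to 3.25.

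The factor s + (1 − s) × f cancels from the ratio when s and f are the same in both arms. It does not cancel from the difference.

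**Chance imbalance**

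Randomisation is stratified by T2DM status (SAP 2.3), so s should be close across arms. With 26 against 24 T2DM participants out of 49, f = 0 and equal T2DM rates, the spurious ratio is (26/49) / (24/49) = 1.08.

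**Denominators after a split**

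Per arm of 49, T2DM participants number 49 × 0.40 = 19.6 to 49 × 0.65 = 31.85, or about 20 to 32. Those without T2DM number about 29 to 17.

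**The case against.** A reader might infer that the pooled rates cannot be interpreted at all. The documents do not support that. Treatment is double-blind, metering follows T2DM status and not arm, and T2DM status is a randomisation stratum. Ratios between arms survive when f is zero or similar across arms. This part of the objection stands and limits the point to absolute incidence, rates and differences.

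A reader might also infer that a near-zero rate without T2DM would show only absence of measurement. That too goes beyond the documents. All participants are taught the symptoms, and Level 3 can be recorded in anyone. Protocol Appendix 4 accepts laboratory glucose, which is in the chemistry panel, and participants newly diagnosed with T2DM start self-monitoring (Protocol 6.5.1.1). A low rate may also reflect truly low risk, and the data would not separate the two explanations. What remains is under-ascertainment: the Schedule of Activities has 10 post-dose chemistry panels through Visit 801, at fasting visits, and these are unlikely to catch brief episodes.

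Pooling is inferred from the safety-set default and is not stated outright, and the summary itself is conditional. Protocol 9.4.7 and the open-ended list in SAP 3.15 would permit a split. Neither commits to one for hypoglycaemia.

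Finally, this is a descriptive table in a phase 2 study, and the split could be run at any time. That is true, and it is also why specifying it now costs almost nothing.

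**Conclusion.** The point holds for absolute measures. Followed as written, SAP 3.14.3.1 with the safety-set default gives a pooled incidence, rate and risk difference below those in T2DM participants. The T2DM rate would be 1.54 to 2.5 times the pooled rate at f = 0 and about 1.35 to 1.8 times at f = 0.25. The f = 0 figures are the extreme case. The values of f and the similar follow-up by diabetes status are assumptions; only the share of 40% to 65% comes from the documents.

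The problem is mainly with Level 2. No systematic bias in the rate ratio between arms follows from it, provided that f is zero or similar across arms. If the effect of treatment differs by diabetes status, only a split would show it.

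**What to change.** In SAP 3.14.3.1:

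1. Report incidence, episodes and rate per 100 patient-years for Level 2 and for Level 3, by treatment group within baseline T2DM status. Use separate patient-year denominators and make the T2DM group the main display.
2. Add a footnote that participants without T2DM were not routinely given meters, so their Level 2 counts are under-ascertained.
3. List the background glucose-lowering therapy of participants with events, descriptively. Do not compare arms within users of rescue insulin: rescue starts after randomisation and may depend on treatment, and the cells would be very sparse.

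SAP 3.14.1.1 sets a precedent by limiting the denominator for sex-specific events to the sex concerned.

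The cost is one further table split and a footnote. T2DM status is already recorded as a stratum, so no new data are needed. The downside is smaller denominators, about 20 to 32 T2DM participants per arm of 49, so the estimates will be less precise.

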3.14.3.2. Hepatic Safety

3.14.3.2.1. NASH-Related Clinical Events

NASH-related clinical events will be considered as AESI. The counts and percentages of participants with the event will be summarized by treatment.

A listing of participants with adjudicated NASH-related clinical events will be provided. The listing will include patient identification including the treatment, site number, date of the event, sex, time from first dose of study drug to the event, time from last dose of study drug to the event (if patient had discontinued study drug), and adjudicated description of the event (if available).

3.14.3.2.2. Hepatobiliary Disorders

Hepatobiliary disorders will be considered as AESI. The counts and percentages of participants with treatment-emergent potentially drug-related hepatic disorders will be summarized by treatment using the MedDRA SOC and PTs. Detailed searching criteria can be found in Appendix 1 (Section 6.1).

A listing of participants with treatment emergent hepatobiliary disorders may be provided if deemed necessary.

3.14.3.2.3. Drug-Induced Liver Injury (DILI)

Adjudicated DILI events will be considered as AESI. The counts and percentages of participants with the event will be summarized by treatment. A listing of participants with DILI events may be provided if deemed necessary.

3.14.3.2.4. Liver Enzymes

Analyses for laboratory analyte measurements are described in Section 3.14.4. This section describes additional analyses of liver enzymes.

The counts and percentages of participants with the following elevations in hepatic laboratory tests at any time during the treatment period and during the entire study including follow up period will be summarized between treatment groups:

- The counts and percentages of participants with an ALT measurement 1 or more times (1x), 3 or more times (3x), 5 or more times (5x), and 10 or more times (10x) the central laboratory ULN will be summarized for all participants with a postbaseline value and for subsets based on various levels of baseline value.
 - participants whose nonmissing maximum baseline value is $\leq 1x$ ULN

- participants whose maximum baseline is >1 x ULN, and
- participants whose baseline values are missing.
- The counts and percentages of participants with an AST measurement 1 or more times (1x), 3 or more times (3x), 5 or more times (5x), and 10 or more times (10x) the central laboratory ULN during the treatment period will be summarized for all patients with a postbaseline value and for subsets based on various levels of baseline, as described above for ALT.
- The counts and percentages of participants with a TBL measurement 1 or more times (1x), 2 or more times (2x), the central laboratory ULN during the treatment period will be summarized for all participants with a postbaseline value, and for subsets based on various levels of baseline values:
 - participants whose nonmissing maximum baseline value is ≤ 1 x ULN
 - participants whose maximum baseline is >1 x ULN, and
 - participants whose baseline values are missing.
- The counts and percentages of participants with a serum ALP measurement 1 or more times, 2 or more times (2x) the central laboratory ULN during the treatment period will be summarized for all participants with a postbaseline value and for the subsets described above to TBL.

Maximum baseline will be the maximum non-missing observation in the baseline period. The maximum value will be the maximum non-missing value from the postbaseline period. Planned and unplanned measurements will be included. Evaluation of drug induced serious hepatotoxicity plots will be performed to show the relation between maximum postbaseline ALT (ULN) versus maximum postbaseline TBL (ULN), and maximum postbaseline AST (ULN) versus maximum postbaseline TBL (ULN).

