#### **Medical Conditions**

- 14. Alcohol consumption >14 units/week for women and >21 units/week for men
- 15. Fibrosis stages 0 and 1 according to the NASH CRN scoring system on liver biopsy
- 16. Cirrhosis (fibrosis stage 4)
- 17. Platelet count <150,000/mm^3
- 18. Evidence of other forms of chronic liver disease:
  - a. Alcoholic liver disease
  - b. Hepatitis B as defined by presence of hepatitis B surface antigen (HBsAg)
  - c. Hepatitis C as defined by presence of hepatitis C virus (HCV) RNA or positive hepatitis C antibody (anti-HCV). Participants treated for hepatitis C (and diagnosed as cured) must have an RNA test at screening and also be RNA negative for at least 3 years prior to screening in order to be eligible for the study
  - d. Primary biliary cholangitis as defined by the presence of at least 2 of the following:
    - i. Biochemical evidence of cholestasis based mainly on alkaline phosphatase (ALP) elevation
    - ii. Presence of antimitochondrial antibody
    - iii. Historical evidence of nonsuppurative destructive cholangitis and destruction of interlobular bile ducts
  - e. Evidence of autoimmune liver disease as defined by compatible liver histology
  - f. Primary sclerosing cholangitis
  - g. Current drug-induced liver disease as defined on the basis of typical exposure and history
  - h. Suspected or proven liver cancer
  - i. Any other type of liver disease other than NASH
- 19. Transferrin saturation >50%, except when it has been demonstrated that a diagnosis of hemochromatosis has been excluded by genetic testing and when a previous liver biopsy has demonstrated no evidence of iron overload
- 20. Clinical evidence of hepatic decompensation as defined by the presence of any of the following abnormalities:
  - a. Serum albumin <3.5 g/dL
  - b. International normalized ratio (INR) >1.3

- c. Direct bilirubin > upper limit of normal (ULN) at screening
- d. History of esophageal varices, ascites, or hepatic encephalopathy
- 21. ALT or AST levels >5 times upper limit of normal (ULN) at screening
- 22. ALP  $\geq$ 1.5 the ULN at screening
- 23. Inability to safely obtain a liver biopsy
- 24. History of biliary diversion
- 25. Known positive for human immunodeficiency virus infection
- 26. Active, serious medical disease with likely life expectancy <5 years
- 27. Active substance abuse including oral, inhaled or injection drugs in the year prior to screening

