# 8.2.4.2. Hepatic Safety Monitoring

Participants with NASH may have normal or elevated ALT and fluctuations of ALT are part of the natural course of the disease. Therefore, assessment of possible drug-induced liver injury (DILI) must take into account the baseline ALT (Regev et al. 2019). Possible DILI will be adjudicated by a committee of physicians external to Lilly with hepatic expertise. This committee will be blinded to study assignment. Additional clinical and laboratory monitoring (Appendix 3 Section 10.3) is required if a participant experiences any of the following elevations of liver tests while in the study.

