### For participants with baseline ALT $\geq$ 1.5 X ULN and normal baseline bilirubin:

- Elevation of ALT  $\ge$ 3 X baseline or  $\ge$ 300 U/L (whichever occurs first)
- Elevation of ALT ≥2 X baseline or ≥300 U/L (whichever occurs first) and presence of severe fatigue, nausea, vomiting, right upper quadrant pain
- Elevation of ALP >2 X ULN
- Elevation of TBL >2 X ULN

Baseline ALT is derived from an average of 2 pretreatment ALT measurements at least 2 weeks apart. Elevated baseline is defined as ALT  $\geq$ 1.5 X ULN. In participants with a sizable stable decrease in ALT (>50% of the baseline value) during treatment, a new baseline, corresponding to the ALT nadir, should be established on an individual basis for subsequent determination of a possible DILI signal.

For participants with Gilbert's syndrome, the criterion of elevation of TBL  $\ge 2X$  ULN should be replaced by a doubling of direct bilirubin or increased INR to > 1.5.

If a study participant meets any of the above criteria during the study, liver testing (Section 10.3) should be repeated within 48 to 72 hours including ALT, AST, ALP, TBL, direct bilirubin, gamma-glutamyl transferase, and creatine kinase to confirm the abnormality and to determine if it is increasing or decreasing. If the abnormality persists or worsens, clinical and laboratory monitoring should be initiated by the investigator and in consultation with the study medical

monitor. Monitoring of ALT, AST, TBL, and ALP should continue until levels normalize or return to approximate baseline levels.

Additional safety data should be collected via eCRF if 1 or more of the following conditions occur:

- participant meets any of the above criteria that trigger additional hepatic safety monitoring on 2 or more consecutive blood tests
- participant discontinued from treatment due to a hepatic event or abnormality of liver tests
- hepatic event considered to be an SAE

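### The SAP counts ALT elevations and draws its hepatotoxicity plots only in ULN multiples, so the contrast between arms partly measures ALT lowering; counts relative to baseline and nadir, as the protocol uses, should be added

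*SAP*

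**What the plan says.** **SAP 3.14.3.2.4 (Liver Enzymes).** ALT is counted at 1, 3, 5 and 10 times ULN, the last being "10 or more times (10x) the central laboratory ULN will be summarized for all participants with a postbaseline value". AST is treated the same way. The counts are repeated "for subsets based on various levels of baseline value": maximum baseline at or below 1× ULN, above 1× ULN, or missing. The hepatotoxicity plots set maximum ALT or AST against maximum total bilirubin (TBL), all in ULN units. Nothing in the section is a multiple of baseline or of nadir.

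**Protocol 8.2.4.2 (Hepatic Safety Monitoring).** The principle is that "assessment of possible drug-induced liver injury (DILI) must take into account the baseline ALT". Baseline ALT is the mean of two pretreatment values. The ALT monitoring triggers are:
- baseline below 1.5× ULN: ≥5× ULN, or ≥3× ULN with symptoms;
- baseline at or above 1.5× ULN: ≥3× baseline or ≥300 U/L; with symptoms, ≥2× baseline or ≥300 U/L.

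After a stable fall of more than 50%, "a new baseline, corresponding to the ALT nadir, should be established on an individual basis".

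**Protocol 5.2** excludes "ALT or AST levels >5 times upper limit of normal (ULN) at screening", so ALT up to 5× ULN may enter. **Protocol 2.2** reports significant ALT decreases from baseline at every tirzepatide dose in the earlier type 2 diabetes study, without their size.

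**The concern.** The protocol and the SAP measure on different scales. In this population a fixed ULN threshold can be met without any rise: a participant who enters at 3.5× ULN and stays there is in the ≥3× row. If the drug lowers ALT, such participants leave the row in the active arms and remain in it on placebo, whatever the frequency of injury.

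The baseline split does not match the protocol's. It uses the maximum baseline value and a cut at 1× ULN, where the protocol uses the mean of two values and a cut at 1.5× ULN. The stratum above 1× ULN still runs up to the 5× ULN entry limit.

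At stake is how these tables are read. Fewer elevations on tirzepatide could be taken as evidence of hepatic safety when part of the difference is the expected effect on ALT.

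**Working it through.** The documents give no hepatic event rate, ULN value, baseline ALT distribution or size of ALT reduction, so there is no planned figure to reproduce. The checks are a conversion of the protocol's triggers and an illustration under stated assumptions.

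**1. Protocol triggers against the original baseline, in ULN units.** For baseline b from 1.5 to 5× ULN:
- 3b runs from 3 × 1.5 = 4.5 to 3 × 5 = 15× ULN;
- 2b runs from 2 × 1.5 = 3 to 2 × 5 = 10× ULN;
- 300 U/L is at least 3× ULN for any ULN up to 300/3 = 100 U/L.

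Below 1.5× ULN the triggers are themselves 3× and 5× ULN. All of them fall in the SAP's ≥3× row. What that row lacks is specificity: at baseline 2× ULN it needs only a 3/2 = 1.5-fold rise, and at 3× ULN or more it needs none.

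**2. Triggers after a fall in ALT.** If the multiple-of-baseline rule is applied to the nadir, 3 × nadir is below 3× ULN whenever the nadir is below 1× ULN:
- baseline 2.0, fall 60%: nadir 0.8, 3 × 0.8 = 2.4× ULN, not in the row;
- baseline 3.0, fall 70%: nadir 0.9, 3 × 0.9 = 2.7× ULN, not in the row;
- baseline 4 to 5, fall 50 to 70%: nadir 1.2 to 2.5, 3 × nadir = 3.6 to 7.5× ULN, in the row.

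Protocol 8.2.4.2 also defines an elevated baseline as ≥1.5× ULN. If a nadir below that moves the participant to the ULN criteria, the first two cases are not triggers at all. The protocol does not say which applies.

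**3. Illustration of the contrast between arms.** Assumptions: baseline ALT lognormal, median 1.4× ULN, log-SD 0.55, capped at 5×; within-person log-SD 0.20; 10 post-baseline values; injury, a tripling of current ALT, in 3% whatever the arm. The last column uses 196/4 = 49 per arm.

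| ALT lowering | ≥3× ULN, all | ≥3× ULN, baseline >1× ULN | Injured who reach ≥3× ULN | Participants ≥3× ULN per 49 |
|---|---|---|---|---|
| 0% | 21.6% | 28% | 73% | 49 × 0.216 = 10.6 |
| 20% | 11.8% | 15% | 56–58% | 49 × 0.118 = 5.8 |
| 35% | about 6% | 8% | 42–44% | 49 × 0.06 = 2.9 |
| 50% | 1.8% | 2% | 25–26% | 49 × 0.018 = 0.9 |

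True injuries are 49 × 0.03 = 1.5 per arm in every line. With no lowering, injured participants make up 0.03 × 0.73 / 0.216 = about 10% of the row.

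A second set of inputs (no injury; median 1.0 to 1.6× ULN; between-person log-SD 0.5; within-person log-SD 0.2 to 0.3; 11 post-baseline values) gives 6–36% at ≥3× ULN with no lowering, 2–21% with 20% and 0.4–7.5% with 40%. In the stratum above 1× ULN the figures are 10–41%, 4–24% and 0.7–9%.

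**4. What a baseline-relative count would do.** With the inputs of step 3 and no lowering, uninjured participants flagged fall from 20% at ≥3× ULN to about 0% at ≥3× the protocol's reference and about 2% at ≥2×.

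The count also loses sensitivity. A tripling after 20% lowering is 0.8 × 3 = 2.4× pretreatment ALT; after 35% it is 0.65 × 3 = 1.95×. Using mean pretreatment ALT with the nadir reset, injured participants reaching ≥3× were 48%, 18–19%, 13–17% and 39–57% at 0, 20, 35 and 50% lowering (spread between two runs; the protocol does not define a stable fall). At ≥2× they were 95%, 77%, 57% and 73%, with 1.9%, 0.7%, 4.0% and 13.2% of uninjured participants flagged.

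**The case against.** The strongest reply is that the hepatic assessment does not rest on this table. Possible drug-induced liver injury (DILI) goes to a blinded external committee (Protocol 8.2.4.2), and adjudicated cases are counted by treatment (SAP 3.14.3.2.3). The SAP also plans change-from-baseline models (3.14) and laboratory change summaries and shift tables (3.14.4), and it calls the liver-enzyme tables additional. With about 49 per arm and one or two injuries, case review will tell more than a table. All of this stands, and it limits the weight of the point. None of it supplies a per-participant, baseline-relative count by arm: models average over participants, and a low/normal/high shift table shows a tripling from high as no shift.

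Four stronger readings are tempting, and the documents do not support them.
- That the SAP ignores baseline. It has a split, and for baseline ALT below 1.5× ULN its 3× and 5× rows match the protocol's thresholds.
- That the table hides injuries meeting protocol triggers. Step 1 shows that triggers against the original baseline stay in the ≥3× row. Loss is possible only after ALT has fallen, and then only on one reading of an unsettled rule.
- That the ALP cut-offs conflict. The protocol's monitoring trigger is ALP above 2× ULN, close to the SAP's 2× row; the 2.5× and 3× values are interruption or discontinuation criteria in Protocol 7.1.3.
- That a baseline-relative count is immune to ALT lowering. Step 4 shows that it is not, and at 20% and 35% lowering its ≥3× row catches fewer injuries than the ULN row.

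**Conclusion.** The point holds as a gap in the hepatic tables. The SAP's elevation counts and plots omit the baseline-relative view that the protocol requires for assessing liver injury. With entry up to 5× ULN and expected ALT lowering, the ≥3× ULN contrast partly reflects the drug's effect on ALT and can favour the drug. Splitting at 1× ULN does not remove this.

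The direction holds under both sets of inputs. The size (for example 21.6% against 1.8% with equal injury at 50% lowering) depends on an assumed ALT distribution, within-person variation and reduction, none of which is in the documents. A reader might infer that ALT lowering will be reported as hepatic safety or that injury will go unseen. Given adjudication and site monitoring, neither follows. This is a cheap improvement, not a flaw in the hepatic assessment as a whole.

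**What to change.** In SAP 3.14.3.2.4 keep the ULN tables and add, by treatment and by mean pretreatment ALT below 1.5× versus at or above 1.5× ULN:
- the number of participants meeting the Protocol 8.2.4.2 triggers, with symptom-dependent triggers in their own row, because nausea and vomiting are common on tirzepatide (Protocol 6.5.2);
- the number with ALT ≥2× and ≥3× mean pretreatment ALT;
- separately, the number with ALT ≥2× and ≥3× nadir, with the coding of a stable fall written down;
- an ALT-versus-TBL plot in multiples of baseline.

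State that both sets are read together with adjudicated DILI. The new tables should not be the sole basis of the hepatic statement.

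Protocol 8.2.4.2 must also be reconciled on which criteria apply once the nadir is below 1.5× ULN, since the trigger count depends on it.

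Cost: SAP wording and programming on laboratory data already collected, plus linkage to symptom records for the symptom-dependent triggers; no change in conduct. The downside is a second set of liver tables. Its baseline-based counts also lose sensitivity under moderate ALT lowering, and the rows that use the nadir can flag ordinary variation.
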